We will conduct this study with a diverse population drawn from 3 hospitals at UW Medicine, including a university hospital (UW Medical Center, UWMC), a county, safety-net hospital (Harborview Medical Center, HMC), and a community hospital (Northwest Hospital and Medical Center, NWHMC). UWMC provides specialist care for the Pacific Northwest region and has 529 acute care beds and 75 ICU beds. HMC is operated by the University of Washington and has 413 acute care beds and 94 ICU beds. HMC is the only Level 1 Trauma Center serving five states, and its mission population includes inner city poor, recent immigrants, and persons with HIV/AIDS. NWHMC is a community hospital with 218 acute care beds and 15 ICU beds, serving north Seattle with a large geriatric and nursing home resident population. Our prior studies have included each of these sites.^{29,30,79} These 3 sites offer the advantage of caring for diverse patients while also using a unified EHR incorporating EPIC systems into a platform we have been able to access and use.¹⁶⁻²¹

c) Patient population

Eligible patients over 55 will be identified by ICD-10 codes for one or more of the nine chronic conditions used by the Dartmouth Atlas:¹³⁴ dementia, malignant cancer/leukemia, chronic pulmonary disease, coronary artery disease, heart failure, chronic liver disease, chronic renal disease, diabetes with end-organ damage, and peripheral vascular disease. These nine conditions account for 90% of deaths among Medicare beneficiaries in the US.^{135,136} To increase inclusivity of important and under-studied populations, we will also include all hospitalized patients over age 80. Among patients meeting these criteria, we will include only those with no identified documentation of goals-of-care discussions during the current hospitalization and prior to enrollment. For Trial 2, eligible patients or their surrogates will have sufficient English language proficiency to complete surveys.

d) Description of participants

We will collect the following information about study participants.

Patients: Age, race, ethnicity, sex, comorbidities and acute severity of illness including the National Early Warning Score (NEWS). For Trial 2, we will additionally collect education, marital status, health status (SF-1) and income.

Families: Age, race, ethnicity, sex, education, marital status, health status (SF-1), relationship to patient, living situation related to patient.

Clinicians: Age, race, ethnicity, sex, education.

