Additional outcomes for both trials, obtained from the EHR, include utilization metrics associated with intensity of care (i.e., any ICU admissions, any ED visits, any palliative care consultations, and ICU- and hospital-free days); these outcomes will be assessed at 30 and 90 days after randomization. ICU- and hospital-free days are defined as the number of days alive and outside of the ICU (or hospital) within the specified time period after randomization (i.e. 30 days or 90 days).^{22,23} We will also examine the following outcomes: 1) time to first goals-of-care discussion during the 30 days after randomization; 2) occurrence of any hospital readmissions within 7 and 30 days after discharge from the index hospitalization; and 3) mortality status at 90 days and 1 year after randomization. Costs of care during hospital admission and 30- and 90-days following randomization will be obtained from institutional billing systems. Washington State death certificate data will be used to examine mortality after hospital discharge (Table 1).

b) Outcomes derived from patient- and family-reports (Trial 2 only):

Additional outcomes for Trial 2 will be obtained from patient or family surveys. Surveys will be completed targeting three time points: 1) baseline; 2) 3-5 days after randomization; and 3) 4-8 weeks after randomization. Surveys may be completed in person, online, by mail, or by phone, based on respondents' preferences.

Occurrence and quality of discussions: We use previously validated items to assess the occurrence and quality of goals-of-care communication during the hospitalization after randomization.^{9,24-30} Communication occurrence is assessed with a single item.^{9,25} Quality of goals-of-care communication is assessed with the end-of-life communication scale (QOC_eol) of the Quality of Communication (QOC) survey, developed from qualitative interviews and focus groups with a diverse group of patients, families, and clinicians.^{24,26,28}

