## Secondary outcomes:

- Timing of goals-of-care discussion during the 30 days after randomization.  
Cox proportional hazards model:  
Outcome coded as for the primary analysis.  
Time = observation time (elapsed days between randomization and whichever came first: observed discussion, death, 30 days after randomization). Censored if outcome=0.
- Mortality at several time points:  
Outcome = death (0=alive at date of mortality status evaluation, 1=died by date of mortality status evaluation)  
TIME POINT #1: death outcome measured from EHR data for the 30 days after randomization.  
TIME POINT #2: death outcome measured from EHR data at time of index hospitalization discharge. (All patients have been discharged from their index hospitalization.)  
TIME POINT #3: death outcome measured from EHR data pulled for analyses on 2/7/22.  
TIME POINT #4: death outcome measured from death certificates covering the year after randomization.  
(a) Linear regression with robust standard errors (logistic regression as additional analysis in case reviewers request it).  
(b) Cox proportional hazards model of time to death.  
The time variable will represent the elapsed days between randomization and whichever came first: death or the date on which mortality status is assessed. Censored if death = 0.
- EHR documentation of whether patient received any ICU care in the 30 days (and also in the 90 days) after randomization  
Linear regression with robust standard errors (logistic regression as additional analysis in case reviewers request it): outcome = 0 if no documentation of ICU care during period of interest; 1 if ICU care occurred during that period
- EHR documentation of whether patient had any ED visits in the 30 days (and also in the 90 days) after randomization  
Linear regression with robust standard errors (logistic regression as additional analysis in case reviewers request it): outcome = 0 if no documentation of ED visits during period of interest; 1 if ED visits occurred during that period

- EHR documentation of any palliative care consultation in the 30 days (and also in the 90 days) after randomization  
Linear regression with robust standard errors (logistic regression as additional analysis in case reviewers request it): outcome = 0 if no documentation of palliative care consultation during period of interest; 1 if PC consultation documented during that period

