- EHR documentation of any hospital readmission within specified windows (7 days and 30 days) after discharge from the index hospitalization (excluding apparent readmissions that actually represented hospital transfers):  
Linear regression with robust standard errors; (logistic regression as additional analysis in case reviewers request it): outcome = 0 if no documentation of readmission during period of interest; 1 if readmission occurred during that period.
- Days out of the ICU and alive during specified periods (30 days and also 90 days) after randomization:  
Coding procedure:
  - Step 1: Compute the number of days alive during the period  
If patient died before the end of the period: number of days between randomization and death; If patient alive at the end of the period, number of days in period (30 or 90).
  - Step 2: Compute the number of days in the ICU during the period.
  - Step 3: Outcome measure = days alive minus days in the ICU.

Days-alive and days in ICU will be computed using only the DATES of randomization, death, and ICU admission and discharge. (Times will be ignored.)  
Primary analysis: Linear regression with robust standard errors (logistic regression as additional analysis in case reviewers request it)
- Days out of the hospital and alive during specified periods (30 days and also 90 days) after randomization:  
Coding procedure:
  - Step 1: Compute the number of days alive during the period  
If patient died before the end of the period: number of days between randomization and death; If patient alive at the end of the period, number of days in period (30 or 90).
  - Step 2: Compute the number of days in hospital during the period.
  - Step 3: Outcome measure = days alive minus days in hospital.

Days-alive and days in hospital will be computed using only the DATES of randomization, death, and ICU admission and discharge. (Times will be ignored.)  
Primary analysis: Linear regression with robust standard errors (logistic regression as additional analysis in case reviewers request it)

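### The SAP takes 30-day and 2/7/22 deaths from the EHR alone and names no death-date source for free days, although the protocol assigns post-discharge mortality to death certificates

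*SAP*

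**What the plan says.** **Mortality, SAP (Secondary outcomes).** There are four time points. The first is "TIME POINT #1: death outcome measured from EHR data for the 30 days after randomization". The second is status at index discharge, also from the EHR. The third is status in an EHR pull on 2/7/22. Only the last uses another source: "TIME POINT #4: death outcome measured from death certificates covering the year after randomization". At each time point a patient is coded alive or died, with no category for unknown. The Cox model censors a patient not coded as dead on the date when status is assessed.

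**Mortality, protocol (section 5a and Table 1).** The listed outcome is "mortality status at 90 days and 1 year after randomization", and Table 1 gives death certificates as its source. Section 5a adds the general statement that "Washington State death certificate data will be used to examine mortality after hospital discharge". The protocol lists no 30-day mortality outcome, and the SAP has no 90-day mortality time point.

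**Free days.** For both ICU- and hospital-free days the SAP begins with "Step 1: Compute the number of days alive during the period". It credits the whole 30 or 90 days to anyone alive at the end, then subtracts ICU or hospital days. It says that calendar dates are used, including the date of death, but not where that date comes from. Protocol section 5a places free days under this sentence: "Additional outcomes for both trials, obtained from the EHR, include utilization metrics associated with intensity of care".

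**The concern.** A hospital system's record reliably knows about deaths inside that system. It knows about later deaths only if someone reports them. The protocol accepts that its records have limited reach: section 5b adds patient and family reports in Trial 2 to capture care outside the system, and section 10g says that Trial 1 costs elsewhere cannot be seen. Trial 1 has no contact with patients or families, so surveys cannot fill the gap there.

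Under the SAP as written, an unrecorded death after discharge becomes a survivor at the first and third time points. If the same date feeds the free-day calculation, the patient also receives close to the best possible score on an outcome meant to penalise death. The same patient could be alive at day 30 in one analysis and dead on day 10 in the certificate-based one. At stake are the secondary mortality and intensity-of-care results. The 0/1 coding of the primary outcome does not use death.

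**Working it through.** No figure in the plan depends on this point, so there is nothing to reproduce. The check compares the sources and then sizes the error under stated assumptions.

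**1. Sources side by side**

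| Outcome | Protocol source | SAP source |
|---|---|---|
| Mortality, 30 days | not listed; general post-discharge sentence points to certificates | EHR |
| Mortality, 90 days | certificates | absent |
| Mortality, 2/7/22 | not listed; same general sentence | EHR |
| Mortality, 1 year | certificates | certificates |
| Free days, 30 and 90 days | EHR | death-date source not named |

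**2. One patient.** Let P be the window, d the day of discharge and t the day of an unrecorded death, with no later hospital days. True hospital-free days are t − d. The recorded value is P − d, so the excess is P − t. With d = 3 and t = 10:
- true value: 10 − 3 = 7
- recorded at 30 days: 30 − 3 = 27, an excess of 20
- recorded at 90 days: 90 − 3 = 87, an excess of 80

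**3. Arm means and the contrast.** If a share u of an arm has an unrecorded death on day t, that arm's mean rises by u × (P − t). With the same timing in both arms, the contrast shifts by (u₁ − u₀) × (P − t). The values of u and t are assumptions; the documents give none.

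| P | t | Excess per patient | Arm-mean shift at u = 1%, 3%, 5% | Contrast shift for a 1- or 2-point difference in u |
|---|---|---|---|---|
| 30 | 10 | 20 | 0.2, 0.6, 1.0 | 0.2, 0.4 |
| 30 | 20 | 10 | 0.1, 0.3, 0.5 | 0.1, 0.2 |
| 90 | 20 | 70 | 0.7, 2.1, 3.5 | 0.7, 1.4 |
| 90 | 45 | 45 | 0.45, 1.35, 2.25 | 0.45, 0.9 |
| 90 | 70 | 20 | 0.2, 0.6, 1.0 | 0.2, 0.4 |

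If u and the timing are equal in both arms, the contrast shift is zero.

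**4. Mortality.** Let m be the true 30-day risk and s the share of all deaths that the EHR misses. Recorded risk is m(1 − s). For an assumed m of 5-15% and s of 10-40%:
- recorded risk runs from 0.05 × 0.6 = 3% to 0.15 × 0.9 = 13.5%
- among the 2000 patients planned for Trial 1, the number wrongly coded alive runs from 2000 × 0.05 × 0.1 = 10 to 2000 × 0.15 × 0.4 = 120
- with the same s in both arms, a true risk difference of 0.03 becomes 0.03 × 0.9 = 0.027 down to 0.03 × 0.6 = 0.018

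**5. How steps 3 and 4 fit together.** Step 3 counts missed deaths as a share of patients, and step 4 as a share of deaths. If s is equal but true mortality differs by 0.03, then u differs by 0.03 × s, which is 0.3 to 1.2 points. The 30-day free-day contrast then moves by 0.003 × 10 = 0.03 to 0.012 × 20 = 0.24 days, in favour of the arm with more deaths.

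**The case against.** The strongest reply is that much of this is not a departure from the protocol. That is largely right, and it limits the point in five ways.

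- **30-day mortality is an SAP addition**, openly labelled as EHR-based. The conflict rests on the protocol's general sentence about mortality after discharge, not on a listed 30-day outcome.
- **Free days.** A reader might infer that the SAP overrides the protocol here. It does not: the protocol itself groups free days with EHR outcomes, and the SAP is silent on the death date. The gap lies in both documents, and EHR-only dates are an inference.
- **Direction.** A reader might infer that the prompt moves patients to comfort-focused discharge, that the EHR loses those deaths, and that the bias therefore favours the intervention and hides a mortality signal. No passage states how completely the EHR captures deaths, or where it fails. Washington deaths in the first 30 days still enter the 1-year certificate analysis, with their timing.
- **Catchment.** The line "HMC is the only Level 1 Trauma Center serving five states" might suggest that all three hospitals draw patients from five states. It describes one hospital's trauma role. Certificates from one state may still miss deaths elsewhere, but the certificate source at 1 year is the protocol's own choice.
- **Timing of the data.** The SAP fixes the EHR pull but gives no date for a certificate file that must cover a year. Waiting for it could be more than a trivial delay.

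What stands is that two mortality windows extending past discharge rely on the EHR alone, that unknown is coded as alive, and that the free-day death date has no stated source.

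**Conclusion.** The concern holds as a gap in outcome definition for secondary outcomes. SAP Time Points #1 and #3 conflict with the protocol's general statement on post-discharge deaths, and followed as written they code unrecorded deaths as survivors. For free days the defect is an unnamed source. The day-3, day-10 example shows what follows if that source is the EHR alone.

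The number of patients affected cannot be derived from the documents. The attenuation of a 0.03 mortality difference to 0.027-0.018 assumes that 10-40% of deaths are missed equally in both arms. The free-day shifts of about 0.1-0.4 days at 30 days and 0.2-1.4 days at 90 days assume a 1-2 point arm difference in patients with missed deaths, with the days of death in the table. The sign of that shift cannot be known in advance. The omission of the protocol's 90-day mortality outcome belongs to the same repair, because 90-day free days already need vital status to day 90.

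**What to change.** In the SAP, define one date of death per patient: the earliest date found in either the EHR or the Washington death certificate file already planned for Time Point #4. Use that date for:
- mortality at 30 days, 90 days (restored from the protocol), 2/7/22 and 1 year
- Step 1 of the ICU- and hospital-free day outcomes at 30 and 90 days
- death and censoring times in the Cox models, including the model for timing of goals-of-care discussions, where observation also ends at death.

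Report EHR-only results as a sensitivity analysis, and the count by arm of deaths found only in certificates, so that the reader can see whether capture differed.

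The cost is SAP wording, one merge and some delay. These secondary results either wait for the certificate file or are issued from the EHR, labelled provisional, and updated when it arrives. Deaths outside Washington that the EHR does not know about may still be missed, and the SAP should say so.

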The study comprises two linked, complementary randomized trials. Trial 1, a large pragmatic trial, compares usual care with the clinician-facing Jumpstart for hospitalized older adults with serious illness (target n=2000; ADRD subset, target n=400). Trial 2, a comparative effectiveness trial is a three-arm trial that compares the clinician-facing Jumpstart, the bi-directional, patient-specific Jumpstart and usual care (n=600). Subjects are enrolled from the UW Medicine hospitals (Harborview Medical Center, UW Medical Center - Montlake, UW Medical Center – Northwest). For Trial 1, eligible patients are ≥ 55 years, admitted for a minimum of 12 and a maximum of 96 hours prior to study enrollment to inpatient services, without a documented GOCD during admission, and meet criteria for serious illness; hospitalized patients >80 years are also eligible. For Trial 2, eligible patients meet the same criteria and, in addition, must be sufficiently fluent in English to complete questionnaires and not be under COVID precautions to allow in-person recruitment. For Trial 2, eligible family may include any of the following: legal guardians, durable power of attorney for healthcare, spouses, adult children, parents, siblings, domestic partners, other relatives, and friends. In addition, we will conduct qualitative interviews with key stakeholders including patients/families (n=40, subgroup of patients enrolled for Trial 2) and clinicians (n=50 across Trial 1 and Trial 2).

2) Specific Aims:

Specific Aim 1 (Trial 1): Evaluate the effectiveness of a novel clinician-facing Jumpstart, compared with usual care, for improving the quality of care; the primary outcome is EHR documentation of a goals-of-care discussion during the 30 days after enrollment. Secondary outcomes focus on intensity of care: ICU use, ICU and hospital free days, costs of care during the hospitalization, and 7- and 30-day hospital readmission.

Specific Aim 2 (Trial 2): Evaluate the efficacy of the bi-directional, patient-specific Jumpstart compared to the clinician-facing Jumpstart and usual care for improving quality of care; the primary outcome is EHR documentation of a goals-of-care discussion 30 days after enrollment. Secondary outcomes include: intensity of care outcomes from Aim 1 and patient- and family-reported outcomes assessed by surveys at 3-5 days and

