Costs of care	Intensity of care/intervention costs	EHR: During hospital stay, 30 and 90 days post-randomization.
All-cause mortality at 90 days and 1 year	All-cause mortality	Washington State death certificates
Aim 2 outcomes (not used in Aim 1 since the Trial 1 is a pragmatic trial without contact with patients or family members)		
Patient/family-reported discussion of goals ^{9,25}	Goals-of-care discussion occurrence	Survey: 3-5 days & 4-6 weeks post-randomization

Quality of Communication (QOC) ^{24,26,28}	Quality of communication	Survey: 3-5 days post randomization
SUPPORT question ³¹	Goal-concordant care	Survey: 3-5 days & 4-6 weeks post-randomization
HADS – anxiety and depression ^{36,37}	Symptoms of anxiety & depression	Survey: 4-6 weeks post-randomization
EQ-5D-5L	Health-related QOL	Survey: 4-6 weeks post-randomization
Patient/family reported ED, hospitalization and outpatient utilization	Healthcare utilization	Survey: 4-6 weeks post-randomization
CollaboRATE ⁶⁰	Shared decision-making	Survey: 3-5 days post randomization

6) Analyses

We will follow the intention-to-treat principle for all analyses.

a) Primary Outcome (presence of goals of care discussion within 30 days after randomization)

The effect of intervention on the primary outcome will be quantified by the difference in proportions and evaluated with a linear regression model with robust standard errors. The predictor of interest is randomization arm (Clinician-facing Jumpstart or usual care for Trial 1; or Clinician-facing Jumpstart, Bi-directional Jumpstart, or usual care for Trial 2). The model will adjust for hospital site and ADRD status, since randomization is stratified on these factors. This model assumes the effect of intervention is the same for patients with and without ADRD. We will also include an interaction between randomization arm and ADRD, which allows the effect of intervention to vary by ADRD status and allows evaluation of the effect among those with and without ADRD. We will evaluate the timing of goals-of-care discussions with a Cox proportional hazards model.

b) Additional Outcomes

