This project requires the creation, maintenance, and analysis of a database that includes a variety of measures from multiple sources. This study, like all studies, depends on the quality of the data and therefore systematic data collection, quality control, and data-management procedures will be implemented: 1) protocols for data collection; 2) rigorous training, certification, and periodic re-training of study staff, with ongoing monitoring of adherence to protocols; 3) regular review of questionnaire response rates, respondent burden,⁶⁷ and missing items to identify and correct problems; 4) verification of all data through custom-designed data entry systems; and 5) weekly team meetings to provide feedback to study staff to ensure problems are resolved quickly. To ensure reliability and validity of data, we will use our current methods for training and quality control.⁶⁸⁻⁷² Staff conducting EHR review will undergo the following training: instruction on the protocol, guided practice abstraction, and independent abstraction with reconciliation by a trainer.

9) Protocol modifications

1. Changes to inclusion/exclusion criteria for Trials 1 and 2 (except where noted)
 - a. Lowering the inclusion criteria age from ≥ 65 to ≥ 55 years
 - b. Removing "English speaking" as an inclusion criterion (Trial 1 only)
 - c. Adding hospital admission for a minimum of 12 hours as an inclusion criterion

- d. Removing markers of frailty as an eligibility criterion
 - e. Adding pregnancy, suicide attempt and same-day discharge as exclusion criteria
 - f. Adding COVID-19 as a specific inclusion diagnosis (Trial 1 only)
2. Study design
 - a. For Trial 2, in addition to comparing the bi-directional (survey-based) Jumpstart Guide to the clinician-facing (EHR-based) Jumpstart guide, we will also include a third arm in which patients receive usual care.
 - b. We have increased the target sample size from n=400 to n=600 to accommodate the addition of a third “usual care” arm to the study.
 - c. We have modified the questionnaires that patients receive at baseline such that only patients in the bi-directional Jumpstart arm are presented with items that are used to create the bi-directional (survey-based) Jumpstart Guide. These items are an integral part of the bi-directional intervention and therefore not appropriate for the other arms to complete.
 3. Procedures

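### One-year mortality (SAP Time Point #4) rests on Washington death certificates alone, so deaths in other states, even those known to the EHR, would be counted as survival

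*SAP*

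**What the plan says.** The SAP, under Secondary outcomes, analyses mortality at four time points. The first three use the EHR: 30 days, index discharge, and a data pull on 2/7/22. The fourth is "TIME POINT #4: death outcome measured from death certificates covering the year after randomization". The SAP line does not name a state; the protocol does. Section 5a states that "Washington State death certificate data will be used to examine mortality after hospital discharge", and the Table 1 row for death at 90 days and 1 year lists only "Washington State death certificates".

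For every time point the SAP codes death as 0 for alive and 1 for died at the evaluation date. Cox time ends at death or at the date status is assessed, whichever is earlier, with censoring when death is 0. There is no category for unknown status and no rule combining EHR and certificate deaths.

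On who is enrolled, the opening summary requires patients to be "admitted for a minimum of 12 and a maximum of 96 hours prior to study enrollment to inpatient services", and section 4c says "Eligible patients over 55 will be identified by ICD-10 codes for one or more of the nine chronic conditions". The exclusions added in section 9 ("Adding pregnancy, suicide attempt and same-day discharge as exclusion criteria") do not concern residence either. On where patients come from, section 4b says "HMC is the only Level 1 Trauma Center serving five states" and "UWMC provides specialist care for the Pacific Northwest region".

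**The concern.** The population can include people who live outside Washington, while the one-year death source covers Washington only. Someone discharged to another state who dies there has no Washington certificate. Under the alive/died coding that patient takes the value for alive, and in the Cox model contributes time at risk up to the assessment date. This applies even when the EHR holds the date of death, because EHR deaths feed Time Points #1 to #3 only.

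The plan recognises the same kind of leakage elsewhere. Section 5b adds patient and family reports to capture utilisation outside UW Medicine, and section 10g concedes that outside costs are unavailable. Neither document says anything equivalent about deaths. At stake are the absolute one-year mortality reported for each arm and the risk difference from the linear model.

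**Working it through.** The documents give no one-year mortality, out-of-state share or power for death, so there is no stated figure to reproduce. What follows is an illustration.

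**Inputs**
- Trial 1 size: 2000, 1000 per arm (protocol section 7a).
- q, true one-year mortality: assumed 35%.
- s, share of patients living outside Washington: assumed 5% to 20%.
- d, share of non-residents' deaths that occur outside Washington: assumed two-thirds.
- Residents and non-residents are assumed to have the same mortality, so the share of all deaths that is missed is m = s × d.

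**Absolute mortality.** Recorded mortality is q(1 − m), so the shortfall is q × m.
- s = 5%: m = 0.05 × 0.667 = 0.033. Shortfall 0.35 × 0.033 = 1.2 points, about 23 deaths in 2000.
- s = 20%: m = 0.20 × 0.667 = 0.133. Shortfall 0.35 × 0.133 = 4.7 points, about 93 deaths in 2000.

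Over a wider grid (q from 20% to 40%, m from 2% to 15%), missed deaths 2000 × q × m run from 8 to 120.

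**Risk difference.** With m equal in both arms, the difference is multiplied by 1 − m, a loss of 3% to 13%. A true 6-point difference becomes 0.06 × 0.967 = 5.8 or 0.06 × 0.867 = 5.2 points.

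**Hazard ratio.** Approximate it by the ratio of log survival at one year. Take control mortality of 30%, a true ratio of 0.80 and m = 10%. Intervention mortality is 1 − 0.70^0.80 = 24.8%. The recorded ratio is ln(1 − 0.248 × 0.9) / ln(1 − 0.30 × 0.9) = 0.253 / 0.315 = 0.80. Across the wider grid it stays between 0.80 and 0.81.

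**Power, all patients against Washington residents only.** For 35% versus 41%, two-sided 5% level, normal approximation, power is 79% with no missed deaths.
- s = 5%: 77% for all 1000 per arm with diluted rates; 77% for 950 residents per arm with undiluted rates.
- s = 20%: 70% for all 1000 per arm; 70% for 800 residents per arm.

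Restriction removes the dilution but gives back the gain in lost sample.

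**The case against.** **The effect is small and every magnitude is assumed.** This stands. A true 3-point difference would become 2.6 to 2.9 points (3 × 0.867 to 3 × 0.967). The 95% half-width is about 1.96 × √(2 × 0.35 × 0.65 / 1000) = 4.2 points. Equal loss creates no false difference when there is no true effect.

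**The catchment evidence is indirect.** This stands in part. The five-state statement concerns a trauma role, whereas eligibility rests on chronic illness or age. The same section describes HMC's inner-city mission population and a community hospital serving north Seattle. The second hospital's regional specialist role is closer to the trial population, but no share can be read from it, and 20% across all sites may be too high.

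**Out-of-state deaths are not wholly ignored.** Time Point #3 would include any that the EHR knows of. But it ends on one calendar date, so follow-up differs between patients, and it does not feed Time Point #4.

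**The SAP never says that an unmatched patient is alive.** This is correct. The consequence is inferred from a two-value coding with no alternative offered. One sentence could settle it.

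A reader might infer more than the documents support:
- That one-year death is the trial's sole long-term safety check. Neither document calls mortality a safety outcome, and Aim 1's list of secondary outcomes omits it.
- That the bias differs by arm. Unequal loss would give a spurious difference of q(m0 − m1), where m0 and m1 are the missed shares in control and intervention: for example 0.30 × (0.05 − 0.10) = −1.5 points. Nothing in the documents suggests that the guide alters where patients go after discharge.
- That Washington residents should be the main population. Residence at baseline keeps the comparison randomised, but section 6 commits all analyses to intention to treat, and the restriction gains no power.

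**Conclusion.** The gap is real and worth closing, though it is modest and confined to secondary mortality outcomes. Followed as written, the plan would enter deaths in other states into Time Point #4 as survival to one year, including deaths the EHR has recorded. That understates absolute mortality in both arms and pulls the risk difference slightly toward zero. The hazard ratio is little affected if loss is equal across arms.

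The size cannot be determined from the documents. The 1.2 to 4.7 points of missed mortality and the 3% to 13% dilution depend on the assumed out-of-state share, mortality and place of death, and on equal loss in the two arms. Deaths in Washington, including those during the index stay, are not in question. The protocol's 90-day mortality has the same listed source and the same gap.

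**What to change.** - Keep all randomised patients as the main analysis of Time Point #4.
- State that a death counts in #4, and in the protocol's 90-day mortality, if either the EHR or a death certificate shows it within the window.
- Add a pre-specified sensitivity analysis restricted to patients whose address at the index admission is in Washington. Alternatively, in the Cox model, censor non-residents without a recorded death at their last known EHR contact; this assumes that loss of contact is unrelated to the risk of death.
- Report the number of non-residents by arm, and add a sentence on deaths outside Washington to the limitations in section 10.

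The cost is a few sentences of SAP text and one extra EHR field; address is not in the section 4d list of patient data, so its availability must be confirmed. The sensitivity analysis has a smaller sample. Merging the sources recovers only deaths the EHR knows of, which is why the residence analysis is still needed.
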